11.7 Procedure for data retention

Once the Clinical Investigation Report is signed and validated, the data are archived on a dedicated hard disk file with limited access rights. This specific file is mounted on AXIODIS's OVH server with a

back-up every two months as well as copied to an external disk that will be stored under seal within the premises of AXIODIS. The data are conserved for at least 10 years.

12. Amendments to the CIP

Neither the investigator nor the sponsor may alter the protocol without the authorisation of the other party.

All changes to the protocol are subject to an amendment which must be dated and signed by both parties and must appear as an amendment to the protocol.

Substantial amendments are submitted to the EC and ANSM for approval.

13. Deviation from clinical investigation plan

All protocol deviations will be managed as per the Standard Operating Procedures of the CRO in charge of the study coordination.

A deviation log shall be maintained by the study site. All deviations will be included, as required in the final study report.

Any major deviation from the protocol that has not been previously approved by the sponsor must be reported to the sponsor within 2 working days of the deviation occurrence. Any deviations from the clinical investigation plan that are identified during routine monitoring visits will be reported to the sponsor within 24 hours of being identified.

Corrective and preventive actions and principal investigator disqualification criteria will be described in the monitoring plan.

Major protocol deviations are defined as deviations liable to prevent or change the interpretation of the results of the study. The following deviations are considered major:

- Non-compliance with the inclusion or exclusion criteria
- Non-compliance with treatment
- No collection of middle meatus swab sample at any visit
- Intake of forbidden medication

All other cases will, a priori, be considered as minor deviations.

14. Device accountability

Not applicable for this post market interventional study.

15. Ethical consideration

15.1 Informed consent process

According to Regulation UE 2017/745, ISO 14155:2020 and articles L1122-1 and L1122-2 of Code de la Santé Publique, the Principal Investigator or his/her authorized designee must give all pertinent information relative to all aspects of the research before any study procedure. Participants will have the opportunity to carefully review the information document and ask questions prior to accepting or not to participate in the study. As this investigation is interventional, the consent shall be obtained in writing and the study participation must be documented in the patient medical file.

15.2 Subject privacy

This research falls within the scope of the reference methodology MR-001 relating to the processing of personal health data carried out in the context of a research involving the subject's consent collection. The sponsor has signed a commitment to comply with the provisions of MR-001 (CNIL receipt number: 2222437v0 dated from 21st May 2021).

All records identifying directly and/or indirectly the subject will be kept confidential according to the French law n°78-17 *relative to data processing, files and liberties* and the European Regulation 2016/679 effective as of 25 May 2018 (hereafter the "GDPR") and will not be made publicly available.

The present study will be conducted under Regulation 2016/679/EU of the European Parliament and of the Council of 27 April 2016 on the protection of natural persons with regard to the personal data and free movement of such data (GDPR).

In accordance with GDPR, the Sponsor is the "Controller" and the participating sites, monitors, data managers and statisticians are "Processors". Lallemand Pharma, sponsor of the study, is responsible for the processing of the study data. The Data Protection Officer appointed by Lallemand Pharma: [name], [contact].

Confidentiality of data shall be observed by all parties involved throughout the clinical investigation. All data will be secured against unauthorized access. Subject names will not be sent to the sponsor. Only the patient number will be recorded in the CRF, and if the patient's name appears on any document, it must be obliterated before a copy of the document is supplied to the sponsor. All subject data that appear in reports and publications will be anonymised such that the privacy and confidentiality of each subject is maintained.

To characterize the nasal microbiome by quantitative PCR and 16S rRNA gene sequencing, VAIOMER will receive patient biological samples identified by anonymized sample codes. To ensure that personal data cannot be attributed to specific samples, the decoding index will not be communicated to Vaiomer at any time. Moreover, to protect the integrity and the confidentiality of the data generated by Vaiomer, below are the relevant actions in place:

- **Physical location**

Vaiomer will produce data derived from the biological samples which will be stored on Vaiomer local servers (no cloud storage). As Vaiomer does not own the sequencing machines (MiSeq), the sequencing step itself is performed on a public genomic platform (INRAE) in our close environment. This is realized by Vaiomer staff who is validated beforehand by the platform. Sequencing data is

transferred by encrypted download links to Vaiomer server after data acquisition and purged from the data provider disk after 3 months.

- **Data backup**

Vaiomer storage server is backed up externally daily to a secured data center fully owned by our subcontractor.

- **Access control**

Access to these data is restricted to Vaiomer staff via a password-protected personal account. The computer and storage servers are located in a restricted area through badge access control.

No data processing will be performed outside of the European Union but the data base will be transferred to the sponsor at Massagno in Switzerland. Although outside EU, this country is recognized by the EU as offering an adequate data privacy protection.

To fulfil the requirements of source data verification, the PI will be required to obtain consent from each subject stating that they agree for their medical records to be accessed (this will form part of the consent process). The information document and the consent form provided to patient will include a specific paragraph relative to data privacy explaining the lawfulness of personal data processing conditions and patients rights.

The patients's rights are the followings:

- The right to request access to, rectification, deletion or restriction of processing concerning personal data collected during the study,
- The right to get back all data linked to the research and to forward them to another data processing manager (portability right),
- The right to withdraw consent to data collection at any time and to request a restriction of processing concerning personal data as mentioned in GDPR's article 18. However, the data processing manager keeps the ability to reject such request should this right likely make impossible or seriously compromise the achievement of the research objectives.

These rights can be exercised with the investigator or his designated representative or by contacting the Data Protection Officer appointed by Lallemand Pharma: [name], [contact]

15.3 Insurance policy

In accordance with the provisions of the French law *n° 2012-300 du 5 mars 2012 et son décret d'application n°2016-1537 du 16 novembre 2016*, Lallemand Pharma, has an insurance policy intended to guarantee against possible damage resulting from the investigation (appendix D).

It is advisable to underline that non-compliance with the Research Legal Conditions is a cause for guarantee exclusion.

16. Vigilance

Healsea® Chronic will be used within the intended use covered by the CE-mark.

Pursuant to (EU) 2017/745 Medical Device Regulation, for a post market clinical follow-up investigation of a medical device used within the intended use covered by the CE-mark, requirement of MDR articles 87 to 90 apply (materiovigilance).

This additional procedure “collection of middle meatus swab specimens” is invasive (MDCG 2021-6 Regulation (EU) 2017/745) but no expected risk is associated with this procedure. However, should a serious adverse event related to this additional procedure occur, MDR article 80 shall apply.

16.1 Definitions

Incident means any malfunction or deterioration in the characteristics or performance of a device made available on the market, including use-error due to ergonomic features, as well as any inadequacy in the information supplied by the manufacturer and any undesirable side-effect (MDR 2017/745, article 2 (64)).

Serious incident means any incident that directly or indirectly led, might have led or might lead to any of the following: (a) the death of a patient, user or other person, (b) the temporary or permanent serious deterioration of a patient's, user's or other person's state of health, (c) a serious public health threat (MDR 2017/745, article 2(65)).

Serious public health threat means an event which could result in imminent risk of death, serious deterioration in a person's state of health, or serious illness, that may require prompt remedial action, and that may cause significant morbidity or mortality in humans, or that is unusual or unexpected for the given place and time (MDR 2017/745, article 2(66)).

Expected and foreseeable side effects (MEDDEV 2 12-1 rev. 8)

They meet all the following criteria:

- Clearly identified in the manufacturer's labelling;
- Clinically well known as being foreseeable and having a certain qualitative and quantitative predictability when the device is used and performs as intended;
- Documented in the device master record, with an appropriate risk assessment, prior to the occurrence of the incident and
- Clinically acceptable in terms of the individual patient benefit.

Adverse event means any untoward medical occurrence, unintended disease or injury or any untoward clinical signs, including an abnormal laboratory finding, in subjects, users or other persons, in the context of a clinical investigation, whether related or not related to the investigational device (MDR 2017/745, article 2(57)).

Adverse or intercurrent events are graded as follows:

- Mild: Awareness of signs or symptoms but easily tolerated.
- Moderate: Uncomfortable enough to cause interference with usual activity.
- Severe: Incapacity with inability to work or do usual activity.

Serious Adverse Event means any adverse event that led to any of the following:

- (a) death,
- (b) serious deterioration in the health of the subject, that resulted in any of the following:
 - (i) life-threatening illness or injury,
 - (ii) permanent impairment of a body structure or a body function,

- (iii) hospitalisation or prolongation of patient hospitalisation,
- (iv) medical or surgical intervention to prevent life-threatening illness or injury or permanent impairment to a body structure or a body function,
- (v) chronic disease,

(c) foetal distress, foetal death or a congenital physical or mental impairment or birth defect (MDR 2017/745 Article 2(58)).

16.2 Reporting in the CRF

All serious and non serious incidents/serious and non serious risk of incidents/expected side effects/adverse events (except pre-existing condition but CRS) occurring during the clinical investigation will be reported in the CRF.

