7.3 Secondary Objectives

- To assess the efficacy of Healsea® Chronic in improving health-related quality of life of CRS adult patients.
- To assess the global satisfaction of patients in using Healsea® Chronic nasal spray for CRS.
- Safety: to assess systemic and local tolerance of Healsea® Chronic over the study period.

7.4 Scientific justification and clinical relevance for effect sizes, non inferiority margins or equivalence

Not applicable. This is an exploratory clinical investigation.

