8.1.5.4 Safety

Adverse events, incidents and expected side effects of the medical device will be reported in the CRF at each visit/telephone call.

8.1.6 Arrangements for the monitoring maintenance and calibration of equipment used for genomic analysis

Annual maintenance by the manufacturer is performed on the Freedom EVO 150 (Tecan) and pipetting volumes are regularly controlled. The ViiA 7 Real-Time PCR System (ThermoFisher Scientific) is monthly controlled by Vaiomer staff and annually calibrated by the manufacturer. All handling, measurement and safety equipment (e.g. pipettes, scale, Captair Biocap PCR Workstations, spectrophotometers, safety and fume hoods) is annually controlled by specialized providers.

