10.2 Source documents

The investigator is asked to report in the patient's medical record:

- Mention of the subject's participation in the study
- Demographic data (date of birth, sex, name)
- Past medical and surgical history
- Recent past treatments
- Concomitant treatments
- Clinical assessment
- Date of each study visit
- Change in any of the concomitant treatment
- Any adverse event/incident

and all relevant data according to the investigator's opinion.

In case of computerized medical file, a printout will be edited, dated and signed by the investigator.

Source data are documented on the "source data agreement form".

11. Data management

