6.4. General conventions and/or calculated variables

6.4.1. Subject reference start/end dates

For each subject, the reference dates will be the following:

- The reference start date is the date of inclusion visit.
- The reference end date is the date when subject was determined to have ended the trial.

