11.2. Adverse events

Note: in the following paragraph, for a smoother reading:

- Incidents and adverse events will be referred as adverse events (AE);
- treatment-emergent incidents and adverse events will be referred as treatment-emergent adverse event (TEAE).

AE are coded using the MedDRA dictionary version 25.0. They are classified by System Organ Class and Preferred Term.

An AE will be considered as a TEAE if:

- it was not present prior to the reference start date
- it was present prior to the reference start date and worsened during the study (increase of intensity)
- it reappears after the reference start date (finished before the reference end date)

A given TEAE (according to the MedDRA terminology) will be counted only once per subject. If a subject experienced several AEs in the same SOC/PT, the most severe intensity will be retained for this SOC/PT.

Note: if the intensity/severity is missing, a conservative approach will be adopted and the intensity/severity will be considered as severe.

Missing or incomplete dates will be estimated as described in section §6.4.4 in order to determine the TEAEs, but they will be presented as reported in CRF in the data listings. Generally, an AE for which the onset date is missing or incomplete and does not permit to identify the onset according to the date of the reference start date (i.e. missing onset day and month/year corresponding to the reference start date) will be considered as treatment-emergent.

Tables will present separately:

- **incidents related to the use of the medical device** (described as possibly related, probably related or related with the device in the eCRF),
- **adverse events not related to the use of the medical device**

- Summary of adverse-events

Summary tables will be produced for AEs not related to the use of medical device and for incidents related to the use of the medical device. Tables will be adapted depending on the definition of the type of AE

- number and percentage of subjects with at least one adverse event (AE)
- number and percentage of subjects with at least one AE leading to definitive study device discontinuation
- number and percentage of subjects with at least one AE leading to definitive study discontinuation
- number and percentage of subjects with at least one serious adverse event (SAE)
- number and percentage of subjects with at least one TEAE
 - number and percentage of subjects with one TEAE
 - number and percentage of subjects with two TEAE

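### The CRF rule exempts pre-existing conditions other than CRS without bringing worsening back in, while the SAP counts such worsening as treatment-emergent, so non-device-related events can be under-counted

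*Protocol*

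**What the plan says.** Protocol 16.2 lists what goes into the CRF: incidents, risks of incidents, expected side effects and, last, "adverse events (except pre-existing condition but CRS) occurring during the clinical investigation will be reported in the CRF". The rule does not mention worsening.

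Protocol 16.1 defines an adverse event broadly, as "any untoward medical occurrence, unintended disease or injury or any untoward clinical signs", whether or not it is related to the device.

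SAP 11.2 gives three ways for an event to be treatment-emergent. The second is that "it was present prior to the reference start date and worsened during the study (increase of intensity"), and the third is that it reappears after the reference start date. Neither is limited to CRS. SAP 6.4.1 fixes the date: "The reference start date is the date of inclusion visit".

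The safety objective in Protocol 7.3 is "to assess systemic and local tolerance of Healsea® Chronic over the study period".

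**The concern.** The SAP can classify only what the CRF holds. If the recording rule lets a site leave out a comorbidity that worsened on study, two of the three treatment-emergent criteria cannot be applied to any condition but CRS, and the tables fall short of what the SAP defines. The shortfall goes one way: events are missed, never added. The exemption has no limit by seriousness, so it could also reach serious events. In a small single-arm study with no comparator rate to set the result against, a few missing patients would visibly change the reported percentages.

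**Working it through.** No power, error rate or effect size is involved, so the check is a comparison of texts followed by one line of arithmetic.

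**1. What the exemption covers.** By inclusion criterion 4 (Protocol 8.3.1.1), every patient has CRS at entry. If the parenthesis in 16.2 concerned only stable conditions, restoring CRS would make unchanged CRS an adverse event in every patient. The exception for CRS makes sense only if the parenthesis governs how pre-existing conditions behave during the study. On that reading, worsening of CRS is kept and worsening of anything else is dropped. This is an inference from the wording; 16.2 does not say it outright.

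**2. Recording rule against analysis rule.**

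| Event after inclusion | CRF entry required by Protocol 16.2, read literally | Treatment-emergent under SAP 11.2 |
|---|---|---|
| New condition | Yes | Yes |
| CRS increases in intensity | Yes | Yes |
| Non-CRS comorbidity worsens, device suspected | Yes, as an incident | Yes |
| Non-CRS comorbidity worsens or reappears, judged unrelated to the device | No | Yes |

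Only the last row conflicts.

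**3. Whether another route closes that row.**
- Protocol 8.1.5.4 ("Adverse events, incidents and expected side effects of the medical device will be reported in the CRF at each visit/telephone call") and the visit procedures in 8.4.1 are general instructions. They do not address worsening of an earlier condition.
- Protocol 10.2 puts "Any adverse event/incident" in the patient's medical record. That is source, not the analysis database.
- Medical history is taken at V1 only (flow chart; 8.4.1), so it cannot show later change.
- Protocol 16.3.1 covers incidents and expected side effects. Protocol 16.3.2 covers serious events linked to the swab. A serious worsening judged unrelated to both falls outside each.

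**4. Where the shortfall would appear.** SAP 11.2 separates device-related incidents from other adverse events. The affected outputs are Tables 14.3.2.2, 14.3.2.4 and 14.3.2.6 and the listing of serious adverse events.

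**5. Baseline intensity.** The second SAP criterion compares intensity before and after inclusion. Neither document asks for the intensity of a pre-existing condition at V1; the planned history listing (14.1.2.2) shows terms and dates. Even a recorded worsening would lack its reference value.

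**6. Size per patient.** If N is the Safety Set size, a patient whose only non-device-related event is missed lowers the reported proportion by 1/N. With N = 20, 1/20 = 5 percentage points. Twenty is the target for completers without major deviation (Protocol 8.3.6), not the defined Safety Set (SAP 5), so this is approximate. The documents give no comorbidity or worsening rate, so the number of missed patients cannot be derived.

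**The case against.** The best defence is that 16.2 is silent on worsening and does not forbid recording it. A site could treat the parenthesis as the usual rule that a stable condition is history, see a worsening as a new untoward occurrence under 16.1, and enter it under the general instruction in 8.1.5.4. That is possible, so the accurate statement is that such worsening need not be recorded, and not that it goes unrecorded. But this reading does not explain the exception for CRS, and nothing in the protocol requires a site to adopt it.

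Some stronger readings are tempting, and the documents do not support them.

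- A reader might infer that aggravation of a nasal or airway condition by the spray is removed at source and that a zero is built in. It is not. The parenthesis follows adverse events, while incidents are a separate item in the 16.2 list and by definition (16.1) include undesirable side-effects. They must be notified under 16.3.1, and SAP 11.2 places even possibly related events among device-related incidents. The device-related tables should be largely unaffected. What remains is that this route depends on the investigator's causality judgement in an open study.
- A reader might infer that missed events are lost for good. Source records should hold them (10.2), monitors compare the CRF with source (8.5.2), and concomitant medication is collected at the call and at V2. SNOT-22 at both visits and the symptom-change table (14.2.3) also give some evidence on nasal worsening, though not as coded events.
- A reader might take the mentions of allergic rhinitis, sensitive nose and asthma as describing this cohort. Section 4.1 lists the first two as device indications, and 6.6 names asthma as a subject for further study. The eligibility criteria do not exclude such patients, but nothing says how many enrolled.

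**Conclusion.** The conflict is real and limited in scope. A stated recording rule omits events that the SAP defines as treatment-emergent, namely worsening or reappearance of a non-CRS comorbidity judged unrelated to the device, including serious cases related to neither device nor swab. The effect is possible under-counting in the three non-device-related tables and the serious-event listing.

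The direction needs no assumption about rates, only that some site follows 16.2 literally. The size cannot be estimated from the documents. A range built on guessed comorbidity and worsening rates would only restate the guesses, and would overstate the loss by including worsening that is captured as incidents. The one firm figure is about 5 points per missed patient, assuming a Safety Set of about 20 and no other non-device-related event in that patient.

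The point is worth correcting because the remedy is cheap and the safety objective includes systemic tolerance.

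**What to change.** In Protocol 16.2, replace the parenthesis with: *(except pre-existing conditions that neither increase in intensity nor reappear after the inclusion visit)*. Apply it to all conditions, CRS included, so that worsening of CRS stays reportable and stable CRS does not become an event. Keep to intensity and reappearance, because those are the SAP 11.2 criteria. Carry the wording into the CRF instructions, and record the intensity of ongoing conditions at V1 on the mild/moderate/severe scale of 16.1 so that the second criterion can be applied.

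SAP 12 describes a change made after data review, so collection may already be complete. In that case, check the source records required by 10.2 for worsening or reappearance of non-CRS conditions, and state in the report that these may be under-ascertained.

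The cost is one phrase, one baseline item and matching CRF guidance, or a source check if the study has ended. The downside is a few more events to record and code, and a slightly less favourable event rate.
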